The double-blind will be preserved by allowing research staff not present during the iTBS session to be responsible for randomizing the active and sham coil. Therefore, research staff present during the iTBS session may be responsible for clinical ratings. The sham coil setting is designed to mimic the auditory artifact and scalp sensations evoked by the real coil without stimulating the brain. The blinded coil has two sides that can be placed on the participant's head; one side active and one side sham. These sides look identical to the researcher and the participant but TMS/iTBS pulses are delivered from only the active side. Which side is facing the participant is determined by the TMS machine or by self-application. The TMS operator will use the coil as set up by the research staff not present ensuring that both the operator and the participant will not know the orientation (active or sham) of the coil. However, in experienced participants, the difference between real and sham iTBS, as well as the difference between different intensities of iTBS is likely to be noticeable. The TMS operator is responsible for verifying the correct iTBS sequence is loaded into the TMS stimulator prior to administering an iTBS session. If a CD participant is randomized to the sham-iTBS group, all iTBS sessions will be sham. Each HC participant will be randomly assigned to either sham- or active-iTBS for visit 3 then crossed over to the other iTBS administration for visit 4. Measurement of motor evoked potentials will be identical between active- and sham-iTBS groups. In an attempt to avoid placebo effects, it is emphasized to the participant that the sensation is related to the stimulation of scalp nerves and muscles, and brain stimulation itself cannot be felt. While our sham stimulation does produce a sensation that is comparably uncomfortable in at least some participants and can produce muscle twitches, it is not qualitatively identical to the active iTBS. Therefore, while efforts are taken to preserve the double-blind, it is possible that the participant and/or the experimenter will become unblinded to the treatment condition. Because of

this, a questionnaire assessing the blind will be administered to the participant (Appendix 46) and the iTBS administrator (Appendix 47). Also, an assessment of pain will be administered to the participant (Appendix 46).

6. Discharge Procedures

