Endorsing suicidality on the MADRS is an example of a red flag. If a participant endorses this state while the MADRS is administered, a flag is generated, and usually addressed immediately by the clinician administering the MADRS. If a participant reports suicidal thoughts, the CDW Critical Item Alert System will be initiated following the NIDA SOP. Participants may also endorse acute states of depression or mania while participating in this study. Sleep patterns will be tracked to assess potential sleep deprivation. Significant sleep deprivation, or lack of sleep, may have a clinical impact on participants. If this occurs, the LAI will initiate the intervention protocol. This intervention may include referral and/or discharge from the study if clinically significant.

i. Primary Safety Endpoints and Associated Stop Rules

Three outcomes will be monitored throughout the study as safety endpoints associated with a stop rule. As described below, we will track iTBS-induced seizures,

neurocognitive function, and clinically significant adverse events requiring outside evaluation. Chi-square tests will be calculated to test frequency differences between groups (active iTBS vs sham iTBS) for each of these endpoint measures. Each **stop rule** is described in detail below.

1. **Number of iTBS-induced seizures:** more than 1 iTBS-induced seizure resulting in hospitalization within any 10 consecutive participants who receive iTBS will result in a protocol hold until further evaluation by the PI, FDA, and DSMB. The Blind will be broken for any participant with an iTBS-induced seizure. We will also consult [name], M.D., Ph.D., Director, Neuromodulation Program within the Division of Epilepsy and Clinical Neurophysiology, Department of Neurology, Boston's Children's Hospital and Associate Professor of Neurology at Harvard Medical School. [name] is a member of our DSMB and possesses the necessary clinical expertise to evaluate the proposed safety endpoints. No new iTBS sessions will be administered to any participant once this stop rule is enacted until evaluation of the events is concluded and it is deemed appropriate to proceed. However, participants who have completed their iTBS treatments may be scheduled for Contingency Management (CM), MRI scan, or follow-up visits.

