2. **Cognitive performance on Trails B:** Neurocognitive function will be assessed with Trails A and B before and after each iTBS day. Although Trails A and B are usually administered in sequence, **only Trails B** will be evaluated in relation to this stop rule. A completion time for Trails B greater than 90 seconds¹⁶⁹ is considered abnormally long. Therefore, **if a participant requires more than 90 seconds to complete Trails B after iTBS, the following steps will be taken:**
 - a. The participant will rest and be observed for 60 minutes after completion of post-iTBS Trails B.
 - b. Trails A and B will be administered again after the 60 minute timeout period.

- c. A score to complete Trails B a second time greater than 90 seconds will call for the MAI (or covering clinician) to evaluate the participant.
- d. If the MAI (or covering clinician) deems outside evaluation or treatment is necessary, the participant will be discharged from the study and appropriate steps will be taken to seek an outside evaluation/intervention (e.g., an ER visit). The Blind will be broken for this participant at this time.

If more than 1 neurocognitive event identified with Trails B is seen within any 10 consecutive participants, the protocol will be put on hold until further evaluation by the PI, FDA, and DSMB. As above, [name] will be consulted for his evaluation of the stop rule; CM, MRI scan, and follow up visits, may continue but iTBS will not be administered until the hold is resolved.

- 3. **Clinically significant adverse events (i.e. adverse events that require referral for further evaluation) likely related to iTBS.** For example, a mild headache after iTBS that resolves spontaneously or with over-the-counter medication will not be considered clinically significant. A severe headache that starts during or shortly after iTBS and fails to resolve with time and/or OTC intervention would prompt referral to an Emergency Department and will be considered clinically significant.
 - a. If more than 1 clinically significant adverse event related to iTBS administration and having similar clinical features is seen within any 10 consecutive participants, the protocol will be put on hold until further evaluation by the PI, FDA, and DSMB. As above, [name] will be consulted for his evaluation of the stop rule; CM, MRI scan, and follow up visits, may continue but iTBS will not be administered until the hold is resolved.

ii. Clinical Efficacy Cocaine Use Endpoint

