The greatest concern with iTBS treatment is the possibility of inducing a seizure. The Pilot was successfully completed without seizures. The tolerability parameters implemented in the study are well within recommended applications of iTBS, a form of TMS which has substantial published guidelines. The 1996 and 2008 International Consensus Safety Guidelines describe the maximum safe duration of an rTMS train based on intensity and frequency of the stimulation¹³¹. Since the issuance of these guidelines, the incidence of TMS-induced seizures worldwide is very low, estimated as "rare" ¹³¹. There have been no reports of any participant developing epilepsy or repeated spontaneous seizures after rTMS. All rTMS-induced seizures to date have been transient and self-limiting, without long-term sequela^{131, 132}. Concurrent medication has been implicated as a risk factor in some of the seizures reported with rTMS. Some have suggested that certain medications (e.g. tricyclic antidepressants and neuroleptics), should be contra-indicated in those receiving rTMS¹³¹.

Risk Minimization: There is a small risk of seizures from iTBS; nonetheless, participants will be thoroughly monitored first in the Pilot (completed) then in the Expanded Feasibility Study to guard against potential negative effects of iTBS. Participants will undergo screening which will exclude those with a family history of epilepsy, participants who take medication that can affect the seizure threshold, and participants with recurring fainting spells. Psychotropic medications and use of illicit drugs (other than cocaine) associated with a reduction in the seizure threshold will also be exclusionary in this study. All staff administering iTBS will be trained in BLS. A physician or physician assistant will be available in the building while iTBS sessions are in progress and will be called in the event of any medical issue.

3. Vasovagal Syncope

A small number of vasovagal syncopes have been reported following rTMS stimulation. In a number of the reports on rTMS-induced seizures, it is unclear whether the event was a seizure or syncope¹³¹.

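### For two of the three safety endpoints, the active-versus-sham test counts only events first judged to be caused by iTBS; it should count those events whatever their attributed cause

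*Combined protocol and SAP*

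**What the plan says.** Section IV.C.i (Primary Safety Endpoints and Associated Stop Rules), repeated in the monitoring plan at IX.C.i, names three safety endpoints and states: "Chi-square tests will be calculated to test frequency differences between groups (active iTBS vs sham iTBS) for each of these endpoint measures".

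- **Seizures.** The endpoint is labelled "Number of iTBS-induced seizures". The hold rule is narrower: "more than 1 iTBS-induced seizure resulting in hospitalization within any 10 consecutive participants who receive iTBS will result in a protocol hold". The unblinding rule is not narrowed in that way: "The Blind will be broken for any participant with an iTBS-induced seizure".
- **Trails B.** A completion time above 90 seconds after iTBS starts the procedure. No judgement of cause is part of that threshold.
- **Clinically significant adverse events.** The opening paragraph requires only that the event needs outside evaluation. Item 3 adds relatedness: "Clinically significant adverse events (i.e. adverse events that require referral for further evaluation) likely related to iTBS".

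Section IV.C.ii adds a chi-square for worsening cocaine use, with a threshold in self-reported binge dollars and no relatedness condition.

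All adverse events are accumulated and reported to the IRB (IV.C), and the DSMB has access to any adverse event (IX.F). No all-cause comparison of seizures or adverse events by arm is specified, and no criteria are given for calling an event induced by, or likely related to, iTBS. On the blind, III.G.iii.5 (Sham Stimulation) concedes that "it is possible that the participant and/or the experimenter will become unblinded to the treatment condition".

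**The concern.** Monitoring the safety of iTBS in cocaine-dependent people is Aim 5 (III.C). The sham arm is there to separate the effects of stimulation from background events. A filter by opinion, applied before the arms are compared, puts a judgement in place of part of what randomisation already provides.

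The judgement is awkward in this design. Sham does not stimulate the brain, so a sham event passes the filter only if the assessor thinks stimulation may have been real. Section III.G.iii.5 says the difference between real and sham is likely to be noticeable to experienced participants, and the cocaine-dependent participants are scheduled for 30 sessions. It also allows staff present at the sessions to make clinical ratings. The blind is broken after a seizure judged to be iTBS-induced, and nothing says that the attribution is fixed before the allocation is known.

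Separately, two analysts following the opening paragraph and item 3 could build different numerators for the adverse-event test.

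**Working it through.** The plan states no event rate, power or sample size for the safety tests, so there is no figure of its own to reproduce. The check has three parts: a comparison of definitions, an illustration on assumed rates, and a calculation for seizures.

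**1. Definitions side by side (IV.C.i and IV.C.ii; repeated at IX.C)**

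| Endpoint | Opening paragraph | Numbered item | Causal filter |
|---|---|---|---|
| Seizures | iTBS-induced | iTBS-induced; hospitalisation only in the hold rule | Yes |
| Trails B | neurocognitive function | time above 90 s after iTBS | No |
| Adverse events | needs outside evaluation | needs referral and likely related | In item 3 only |
| Cocaine-use worsening | not applicable | binge dollars above 3 times the previous greatest | Not in the threshold |

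So two of the three safety endpoints carry the filter, and for one of these the text is inconsistent.

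**2. Illustration**

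From the documents: 45 active and 45 sham cocaine-dependent participants (III.E), chi-square test. Assumed: two-sided 0.05 (III.G.vi gives 0.05 for behavioural and questionnaire data only), no continuity correction, and all event risks and attribution shares.

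Let p be the true risk and a the share of events attributed to iTBS. The risk that reaches the test is p × a in each arm. With x and y counted events and m = (x + y)/90, the statistic is

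X² = (x/45 − y/45)² / [m(1 − m)(2/45)].

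The probability of significance is the sum of the two binomial probabilities over all (x, y) with X² > 3.84.

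*Equal attribution, real difference (true risks 30% and 10%)*

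| Share attributed in both arms | Counted risks | Power |
|---|---|---|
| 100% | 30% v 10% | 0.69 |
| 70% | 21% v 7% | 0.51 |
| 50% | 15% v 5% | 0.39 |
| 30% | 9% v 3% | 0.24 |

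With no true difference, equal attribution does no harm to test size: at true risks of 10% to 30%, the false-positive probability is 0.053 to 0.059 with all events counted and 0.049 to 0.059 with half counted.

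*Unequal attribution, no real difference.* Suppose staff attribute 80% of events when they believe the coil is active and 40% when they believe it is sham, and guess the arm correctly with probability g. The attributed share is 0.8g + 0.4(1 − g) in the active arm and 0.8(1 − g) + 0.4g in the sham arm. With a true risk of 10%, each arm has 45 × 0.10 = 4.5 events.

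| g | Shares | Expected counts | False-positive probability |
|---|---|---|---|
| 0.50 | 60% v 60% | 2.70 v 2.70 | 0.056 |
| 0.75 | 70% v 50% | 3.15 v 2.25 | 0.074 |
| 1.00 | 80% v 40% | 3.60 v 1.80 | 0.133 |

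Counting all events at 10% gives 0.059. With shares of 80% and 40%, true risks of 20% and 30% give 0.229 and 0.330.

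*Unequal attribution, real difference.* If the shares run the other way, 40% active and 80% sham, true risks of 30% and 10% reach the test as 0.30 × 0.4 = 12% and 0.10 × 0.8 = 8%. Most of the difference is hidden.

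**3. Seizures.** Table 2 (III.G.iv) records 1 seizure in 16,952 iTBS sessions. The active arm would have 45 × 30 = 1,350 sessions, so 1,350/16,952 = 0.080 expected seizures and a probability of at least one of 1 − exp(−0.080) = 0.077, if that survey rate applied to this population.

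**The case against.** **The blind is the intended protection.** Section III.G.iii.1 says all personnel interacting with the participant are blind to coil assignment, and the blind is assessed in participants and operators. If attribution is equal in both arms, no false difference arises, as the table shows. This stands: the bias is conditional on the blind failing and on beliefs shaping attribution. The loss of power does not need the blind to fail, though it does assume that attribution does not separate true effects from background. An assessor who could make that separation might gain power, but the plan gives no criteria that would let one do so.

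**The illustrated effect is assumed and modest.** Also true. At 75% correct guesses, the arms differ by 3.15 − 2.25 = 0.9 event. For seizures, no event in either arm is the likeliest result under any definition.

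**All adverse events already go to the IRB and DSMB.** They do, which makes the change cheap, but no comparison by arm is attached to that reporting.

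**Referral is itself a staff decision.** This stands, and counting regardless of cause does not remove it.

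**Stronger readings.** From "more than 1 iTBS-induced seizure resulting in hospitalization within any 10 consecutive participants who receive iTBS", together with the statement in V.B.ii.2 that "All rTMS-induced seizures to date have been transient and self-limiting, without long-term sequela", a reader might infer that only hospitalised seizures are compared and that the expected kind of seizure could never be counted. The text does not support this. Hospitalisation appears only in the hold rule; the endpoint label, the tracking sentence and the unblinding rule omit it. Nor do these sections contradict one another: one sets a hold, one reviews past rTMS seizures, and the seizure procedures say when to call for emergency transfer. A reader might also infer that every safety endpoint is filtered by attribution; Trails B and the cocaine-use threshold are not.

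**Conclusion.** The point holds as a cheap improvement to the analysis of two safety endpoints. As written, the active-versus-sham tests for seizures and for clinically significant adverse events may reflect attribution as well as event rates, and the opening paragraph and item 3 disagree on what the adverse-event test counts.

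The size cannot be derived from the documents. On the assumptions shown, power falls from 0.69 to 0.39 when half of the events are attributed in each arm. The false-positive probability rises from 0.06 to 0.13 at a 10% true risk when attribution is 80% in one arm and 40% in the other, which in the guessing model means complete unblinding. It would be too strong to say that the comparison measures attribution instead of event rates: with a sound blind and equal attribution, the test keeps its size.

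**What to change.** In IV.C.i and IX.C.i:

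1. State that the between-arm chi-square counts every seizure, hospitalised or not, and every adverse event requiring referral, regardless of attributed cause and over the same monitoring period in both arms.
2. Report relatedness to iTBS as a secondary, descriptive classification, recorded before any unblinding of that participant.
3. Reconcile the opening paragraph with item 3, so that the adverse-event endpoint has one definition.
4. Leave the protocol-hold rules, including the hospitalisation qualifier, to the sponsor, and state only that the qualifier does not define what the chi-square counts.

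The cost is wording in two duplicated sections. Adverse events are already recorded whatever their cause, so no new data collection is needed. The downside is that some unrelated background events will enter both arms' counts, and referral will remain a staff decision.

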uncomfortable side-effects of iTBS. Headaches and scalp pain usually go away promptly with nonprescription medication, such as acetaminophen. Coil heating will be avoided in the present study by using a cooled coil and by allowing the coil to cool off between treatment sessions. If a participant reports dental pain, iTBS will be stopped. Acetaminophen or other medications may be provided for treatment of pain, if necessary.

5. Acoustic Noise

Rapid excitation of the stimulation coil produces clicks that have resulted in transient increase in the auditory threshold of human participants. This should not occur if earplugs are used. Others have measured auditory thresholds with rTMS which we will use for our iTBS administration. Auditory thresholds were measured before and after 30 sessions of rTMS have been assessed given over 6 weeks in a depression treatment trial¹⁷⁴. All participants wore earplugs during stimulation. No significant mean changes in hearing threshold were detected. Two participants showed small bilateral increases in threshold at mid to high frequencies, which returned to previous levels when retested 1 month later. FDA guidelines require testing of auditory threshold only if participants receive rTMS at a frequency higher than 1 Hz for four or more weeks. Auditory threshold will not be monitored in the current proposed study.

Risk Minimization: Participants will be fitted with earplugs to wear during the study to protect their hearing from the noise of the magnet. Participants with known hearing loss will be excluded. Investigators will ask each participant to report immediately any loosening or detachment of the earplugs during application of iTBS. If a participant reports or if an investigator observes that the earplugs have loosened or fallen out, investigators will immediately stop applying iTBS.

6. Other Complications

Risk Minimization: Reports of manic symptoms occurred exclusively after unilateral or bilateral DLPFC stimulation but the risk for psychiatric complications appears to exist predominantly in participants with pre-existing psychiatric morbidity (all except one report), and in patients who are on antidepressants or antipsychotics. An important means of minimizing risk in the current proposed study is therefore to exclude this population. Participants will be informed of the small risk of transient mania or hypomania, informed of early symptoms to look out for, and instructed to contact the study physician if they believe they are experiencing any such symptoms.

iii. MRI scanning

1. Magnetic Field

When used on appropriately qualified individuals, MRI presents virtually no risk as long as technical scan parameters remain within FDA guidelines. There is no exposure to x-rays or radioactivity. The radio waves used have produced burns (most of these minor) in about one in a million exams. The field of the 3T scanner is higher than that of most clinical magnets and there is a remote chance of other risks associated with the stronger magnetic field that might include temporary dizziness with nausea and flickering light sensations. The magnet may move metal implants in the body, the motion of which could be painful and harmful. Metal implants may also cause burns from the radio frequency energy used. While inside the magnet, participants may experience an acute panic attack due to claustrophobia. Participants may also experience mild, remittable discomfort from lying in the scanner.

Risk Minimization. To ensure adherence to FDA guidelines for MRI, a trained MRI operator who has been instructed in these guidelines performs all machine manipulations. Other preventative measures include assuring that all equipment to be used during imaging sessions is MR compatible, that participants are familiar with the MRI environment (using the mock scanner), and that participants are aware of how to signal the MR operator if they need to do so during the

session. Furthermore, participants are screened prior to each MRI session for any MR contraindications, including metal implants, pregnancy, fear of small, enclosed spaces, and inability to lie still for prolonged periods of time.

2. Acoustic Noise

The sound generated by an MR system usually consists of a series of repetitive pulses. Acoustic noise is a result of the mechanical vibration produced by the gradient coils when the large currents are applied to them to create time varying imaging gradient fields. Some participants may experience temporary, reversible shifts in hearing threshold after MRI.

Risk Minimization: MRI compatible headphones and earplugs will be used for hearing protection. The use of these two devices in combination reduces the noise level to levels much lower than those required by the Occupational Safety and Health Administration (OSHA) regulations (Occupational Noise Exposure – 1910.95, www.osha.gov) regulations for lifetime exposure, and provides effective hearing protection for the participants. Nevertheless, some participants may experience temporary, reversible shifts in hearing threshold after MRI.

iv. Mock Scanner

Potential side effects associated with the mock scanner include mild backache from having to lie still for a prolonged period of time, temporary difficulty hearing soft sounds after the exam, and being uncomfortable being in a small enclosed space.

Risk Minimization. Pre-study screening for history of back problems or claustrophobia will minimize the likelihood of side effect from mock scanning. In addition, participants will be given adequate hearing protection to minimize hearing difficulties resulting from Classification of risk (for the study as a whole).

v. Research Involving NIH Employees as Participants

Potential risks should be considered for NIH staff when participating in an NIH protocol because NIH staff may be a vulnerable class of participants. NIH staff will not be allowed to participate in this protocol.

VI. PROTECTION OF PARTICIPANTS' PRIVACY AND CONFIDENTIALITY

Great care is taken to protect participants' privacy and strict participant confidentiality will be maintained throughout. Participants will be consented in a private setting. Participants will be assigned a code number without personally-identifying information following their first contact in the protocol. This number will be used throughout the experiment and will be on specimen samples, behavioral, physiological archival, fMRI/MRI, and iTBS data. The identity of participants will not be revealed at scientific meetings, in publications or other vehicles of public communication. The PI and co-investigators will use an ID code (e.g., ARC#), which is generated in a secure database on a closed network (Human Research Information System [HuRIS], aka CDW). Access to records in CDW is protected by a system of password-protected accounts and monitored by the Clinical Director (CD). Data downloaded for analysis will be identified only by participant number. A Certificate of Confidentiality is in place for the NIDA IRP and covers this protocol.

A. Medical Records

All medical history information is stored in the CDW database, which is password protected and has limited access. Any paper records are kept in a locked cabinet and access to these files is limited to study personnel, including study investigators, nursing staff and clinicians.

B. Research Records/Data

Paper copies of research records such as 'Run Sheets' (procedural checklists) used by investigators will be kept in study-specific binders. These binders are kept in a locked cabinet, in a locked room, which has limited access. Binders remain in this room at all times, apart from when required for study sessions. At the completion of each session paper records will be returned to the locked cabinet by the investigator or research associate responsible for the experimental session. Electronic research records and/or data (physiological, imaging, behavioral) obtained during experimental sessions is stored on password protected, network drives, or other secure application (e.g., CDW, RedCap, Qualtrics) in line with NIH policies, which have limited access. Data stored on these drives is identified by study number, participant ARC# and/or task. No personal identifiers are stored with the data outside of the participant's clinical research record (CDW).

C. Stored Samples

No biological samples will be stored for future use.

VII. STUDY AGENTS/INTERVENTIONS

This protocol uses iTBS as an add-on treatment intervention. We will use the MagVenture MagPro 100 with MagOption (MagVenture Inc, Alpharetta, GA) machine equipped with a figure-8 coil. This protocol is intended to determine efficacy of iTBS in reducing cocaine use and is participant to CRF Title 21, part 812. An IDE is necessary for this protocol and will be applied for after reviews from SRC and IRB.

The MRI is used as a data collection tool and all sequences and scans conducted are within FDA approved parameters and the scans are not conducted to assess safety or efficacy of the scans themselves.

VIII. PLAN FOR REPORTING UNANTICIPATED PROBLEMS AND ADVERSE EVENTS

NIH OHSRP Policies 801 and 802 (effective July 1, 2019; supersedes SOP 16) will be followed for reportable events and non-compliance.

Please note that the PI is the sponsor for the IDE in this protocol until the sponsorship changes over to the NIDA-IRP's Clinical Director, effective October 1, 2019. The Sponsor will report to the FDA as required.

IX. DATA SAFETY MONITORING PLAN

A. Selection of a Data and Safety Monitoring Mechanism

1. Daily Study Monitoring: Data and safety for this protocol will be monitored by the Principal Investigator and MAI.
2. The FDA has approved an IDE for a “staged study” and reviewed a supplement to the IDE application that contained pilot data (See letter from the FDA). IRB approval of the Expanded Feasibility Study is contingent on the approval from the FDA after review of the pilot data (i.e., up to 20 enrollees to yield 10 participants who complete the two-week iTBS intervention). **[Approved by the FDA December 12, 2018].**
3. Overall Study Monitoring: Data and safety will be monitored by the NIDA-IRP Data and Safety Monitoring Board (DSMB).

B. Frequency of the Monitoring

The DSMB will review after:

1. Five participants complete the Pilot inpatient protocol.
2. Five participants complete the Pilot outpatient protocol. Barring any unforeseen adverse events in the Pilot, recruitment for the Expanded Feasibility Study will commence while the DSMB reviews data collected during the Pilot.
3. Every year, after the first participant receives iTBS treatment in the Expanded Feasibility Study, unless there has not been any iTBS administration in the one year reporting period. However, if that is the case, the DSMB will be notified of the lack of progress with explanation. The DSMB review will be requested one year following the next iTBS administration.
4. If either the primary or secondary stop rules are triggered (described below).

C. Stop or Change Rules

i. Primary Safety Endpoints and Associated Stop Rules

Three outcomes will be monitored throughout the study as safety endpoints associated with a stop rule. As described below, we will track iTBS-induced seizures, neurocognitive function, and clinically significant adverse events requiring outside evaluation. Chi-square tests will be calculated to test frequency differences between groups (active iTBS vs sham iTBS) for each of these endpoint measures. Each **stop rule** is described in detail below.

1. **Number of iTBS-induced seizures:** more than 1 iTBS-induced seizure resulting in hospitalization within any 10 consecutive participants who receive iTBS will result in a protocol hold until further evaluation by the PI, FDA, and DSMB. The Blind will be broken for any participant with an iTBS-induced seizure. We will also consult [name], M.D., Ph.D., Director, Neuromodulation Program within the Division of Epilepsy and Clinical Neurophysiology, Department of Neurology, Boston's Children's Hospital and Associate Professor of Neurology at Harvard Medical School. [name] is a member of our DSMB and possesses the necessary clinical expertise to evaluate the proposed safety endpoints. No new iTBS sessions will be administered to any participant once this stop rule is enacted until evaluation of the events is concluded and it is deemed appropriate to proceed. However, participants who have completed their iTBS treatments may be scheduled for Contingency Management (CM), MRI scan, or follow-up visits.
2. **Cognitive performance on Trails B:** Neurocognitive function will be assessed with Trails A and B before and after each iTBS day. Although Trails A and B are usually administered in sequence, **only Trails B** will be evaluated in relation to this stop rule. A completion time for Trails B greater than 90 seconds¹⁶⁹ is considered abnormally long. Therefore, **if a participant**

requires more than 90 seconds to complete Trails B after iTBS, the following steps will be taken:

1. The participant will rest and be observed for 60 minutes after completion of post-iTBS Trails B.
2. Trails A and B will be administered again after the 60 minute timeout period.
3. A score to complete Trails B a second time greater than 90 seconds will call for the MAI (or covering clinician) to evaluate the participant.
4. If the MAI (or covering clinician) deems outside evaluation or treatment is necessary, the participant will be discharged from the study and appropriate steps will be taken to seek an outside evaluation/intervention (e.g., an ER visit). The Blind will be broken for this participant at this time.

If more than 1 neurocognitive event identified with Trails B is seen within any 10 consecutive participants, the protocol will be put on hold until further evaluation by the PI, FDA, and DSMB. As above, [name] will be consulted for his evaluation of the stop rule; CM, MRI scan, and follow up visits, may continue but iTBS will not be administered until the hold is resolved.

3. **Clinically significant adverse events (i.e. adverse events that require referral for further evaluation) likely related to iTBS.** For example, a mild headache after iTBS that resolves spontaneously or with over-the-counter medication will not be considered clinically significant. A severe headache that starts during or shortly after iTBS and fails to resolve with time and/or OTC intervention would prompt referral to an Emergency Department and will be considered clinically significant.
 - a. If more than 1 clinically significant adverse event related to iTBS administration and having similar clinical features is seen within any 10 consecutive participants, the protocol will be put on hold until further evaluation by the PI, FDA, and DSMB. As above, [name] will be consulted for his evaluation of the stop rule; CM, MRI scan, and follow

up visits, may continue but iTBS will not be administered until the hold is resolved.

ii. Clinical Efficacy Cocaine Use Endpoint

1. **Clinically significant worsening of cocaine use behavior will be evaluated and monitored as follows:** Although neuroplastic changes in brain activity assessed with fMRI is our primary outcome variable of interest, we will measure cocaine use behavior (Appendices 13: Cocaine use, Pattern, and Withdrawal Questionnaire, & 21 Time-Line Follow back) at baseline and longitudinally throughout the protocol. Among the cocaine use behaviors assessed is maximum dollar amount spent during the longest lifetime binge. Chi-square tests will be calculated to test frequency differences between groups (active iTBS vs sham iTBS) for this endpoint measure. If a participant reports a binge amount in dollars that exceeds 3 X the greatest binge dollar amount, the following steps will be taken:
 - a. The iTBS treatment for this participant will be paused
 - b. The participant will be scheduled to return the next day for further evaluation, which will include reassessment of cocaine use behavior
 - i. If the participant reports continued excessive cocaine binge behavior, the participant will be referred for alternative treatment. The Blind will be broken for this participant at this time.
 - ii. If the participant reports a return to their normal cocaine use pattern, they will be scheduled for further evaluation in about 1 week.
 - c. After about 1 week, cocaine use behavior will be re-assessed.
 - i. If the participant reports further episodes of excessive cocaine binge behavior, the participant will be referred for alternative treatment. The Blind will be broken for this participant at this time.

- ii. If the participant reports a return to their normal cocaine use pattern, they will be allowed to continue in the study. Their treatment schedule will be resumed at this point.

As soon as the increase is noted and at each follow-up visit, the MAI (or covering clinician) will assess precipitants to the change in cocaine use behavior to ascertain whether a significant life-event (e.g., death of a family member) could be related to a spike in cocaine use behavior (vs. the iTBS itself). Detailed evaluation of the situation is necessary to understand the clinical ramifications of continuing, or discontinuing, the iTBS administrations. If, at any point, the MAI (or covering clinician) concludes that iTBS was likely responsible for the change in cocaine use, the participant will not resume iTBS treatments.

If the participant has a second episode of excessive use in excess of 3 X their previous greatest binge dollar amount after resuming iTBS treatments, they will be discharged and referred for alternative treatment.

Participants who are to be discharged and referred for alternative treatment will be followed as clinically indicated for up to one month to track their clinical course and facilitate transfer to alternative treatment. The participant will be discharged at this point.

If more than 1 clinically significant worsening of cocaine use behavior is seen within any 10 consecutive participants, the protocol will be put on hold until further evaluation by the PI, FDA, and DSMB. As above, CM, MRI scan, and follow up visits may continue but iTBS will not be administered until the hold is resolved.

